1  
2  
3 **MYOPIA TREATMENT STUDY**  
4 **MTS1**  
5  
6

7 **Low-Dose Atropine for Treatment of Myopia**  
8  
9

10 **STATISTICAL ANALYSIS PLAN**  
11  
12

13  
14 **Version 2.1**  
15 **November 28, 2022**  
16 **Based on Protocol Version v5.1 (April 06, 2020)**  
17  
18

19 **Revision History**

VERSION NUMBER		AUTHOR	APPROVER	EFFECTIVE DATE	REVISION DESCRIPTION (INCLUDING SECTIONS REVISED)
SAP	Protocol				
1.0	V4.0 (Oct 4, 2019)	[name]	[name]	April 27, 2018	Initial version
2.0	V5.1 (April 6, 2020)	[name]	[name]	June 15, 2020	The following revisions from SAP Version 1.0 have been highlighted in this updated version. Section 1 1.It has been specified that if the fully-adjusted model failed to converge, or displayed evidence of estimate instability due to partial aliasing, the race/ethnicity and iris color variables would be combined as follows: East Asian (regardless of eye color), non-East Asian with brown eyes, non-East Asian with non-brown eyes. The number of East Asians with non-brown eye color would be tabulated and reported. 2.The maximum likelihood method is specified for the mixed model. 3.It is specified that the tipping point analysis will be conducted only if more than 10% of primary outcome data are missing. Details of implementing the tipping point analysis have been added.

VERSION NUMBER		AUTHOR	APPROVER	EFFECTIVE DATE	REVISION DESCRIPTION (INCLUDING SECTIONS REVISED)
SAP	Protocol				
					
Section 3 The overall false discovery rate (FDR) in the secondary analyses will be controlled at the 5% level using the two-stage step-up FDR procedure.
 
Section 4 1.It is specified that the subgroup analysis based on baseline age and baseline SER will be in 4 categories based on median split. 2.It is specified that an estimate of the treatment effect within each subgroup and a 95% confidence interval will be obtained for each of the times, 24 and 30 months, by adding a treatment by time by subgroup interaction into the primary analysis model and generating the appropriate contrasts. Each subgroup effect will be estimated separately, one subgroup per model. 3.The overall FDR in the subgroup analyses will be controlled at the 5% level using the two-stage step-up FDR procedure.
 
Section 5 The overall FDR in the additional analyses will be controlled at the 5% level using the two-stage step-up FDR procedure.
 
Section 6 1.In the previous version, it was specified that the average of the item responses at the 6-month visit would be calculated and compared using a Wilcoxon Rank Sum test for difference between the treatment groups. In the current version, it has been updated to comparing the average of the item responses at 24-month visit using a t-test to be consistent with the protocol. 2.The adjustment of FDR has been removed given that there is only one average score for the questionnaire.
 
Section 7 1.Given that by the time sufficient data allowing for an analysis of efficacy or futility for the primary outcome would be possible, all or most subjects are expected to be within 1 year of completing the primary outcome, no formal statistical interim monitoring is proposed. 2.It has been added that the tabulated safety and efficacy data will be reviewed by the PEDIG Data and Safety Monitoring Committee at its biannual meetings,

VERSION NUMBER		AUTHOR	APPROVER	EFFECTIVE DATE	REVISION DESCRIPTION (INCLUDING SECTIONS REVISED)
SAP	Protocol				
					and if any unexpected safety or other issues arise, they can recommend to stop the study at any time.
2.1	V5.1 (April 6, 2020)	[name]  [name] <small>Digitally signed by [name], DN: cn=[name], o=Novartis, email=[contact], c=US, Date: 2022.12.20 17:57:05:00</small>	[name]  [name] I am digitally signing this document. 2022-12-20 17:57:05:00	12-19-2022	
The following revisions from SAP Version 2.0 have been highlighted in this updated version.
 
Section 1
 
Per discussion with [name], the previous sensitivity analysis using multiple imputation has been replaced with an analysis of covariance (ANCOVA) model that compares change in SER between treatment groups at 24 months, while only adjusting for baseline factors as specified in the primary analysis. The rationale of this change was that the percentage of missing outcomes at the primary outcome visit (24 months) was low while, due to the virtual visits implemented for the intermediate visits (6, 12, and 18 months), the number of missing outcomes at those visits was higher. The imputation method previously specified would then primarily impute the outcomes at intermediate visits and would not be an effective check of the effect of missing data assumptions on the primary 24 months analysis. The new sensitivity analysis proposed will be used to assess if including the intermediate visits, which have the highest proportions of missing data, in the primary analysis longitudinal model affects the treatment group comparison of the primary outcome at 24 months.
 
Section 2
 
Based on the same rationale for the change in Section 1 above, the previous sensitivity analysis using multiple imputation has been replaced with an ANCOVA model that compares change in SER between treatment groups at 30 months, while only adjusting for baseline factors as specified in the primary analysis.
 
Section 3
 
1. Per discussion with the study leads, the proportion of participants with <math>\geq 0.5D</math>, 1D, and 2D progression in myopia at 12, 24, and 30 months will now be tabulated.
 
2. Per discussion with [name], the previous analysis calculating relative risk of <math>\geq 1D</math> (or 2D) progression in myopia has been replaced with treatment group comparison of proportions at 12, 24, and 30 months using Barnard's test. The originally proposed method of analysis, an analysis of time to progression using the proportional hazards model, was not feasible due to a relatively large proportion of missing data at interim visits due to COVID. While missing data is still a


VERSION NUMBER		AUTHOR	APPROVER	EFFECTIVE DATE	REVISION DESCRIPTION (INCLUDING SECTIONS REVISED)
SAP	Protocol				
					
problem in the analyses of results of interim visits when using Barnard's test, the 24-month primary time point is largely unaffected, as the amount of missing data is minimal.
 
3.Per discussion with the study leads, to evaluate biologic activity of the drops, and the potential effect of dilute atropine on accommodation, as a post hoc analysis, mean binocular near point of accommodation at 6 months was compared between treatment groups using an ANCOVA model, adjusting for baseline binocular near point of accommodation, age, iris color (brown vs. not brown), and race (East Asian vs. non-East Asian).

20

21 The primary objective of MTS1 is to determine the efficacy of daily low-dose atropine  
22 (0.01%) for slowing myopia progression over a two-year treatment period in children  
23 aged 5 to less than 13 years with myopia -1.00D to -6.00D at the time of enrollment.

24  
25 Participants are randomly assigned 2:1 to the following two treatment groups:

- 26 • Atropine Group: 0.01% atropine eyedrops administered 1 drop to each eye daily for  
27 24 months, followed by 6 months off atropine eyedrops
- 28 • Placebo Group: Placebo eyedrops administered 1 drop to each eye daily for 24  
29 months, followed by 6 months off placebo eyedrops

30  
31  
32 **1. Primary Analysis: Refractive Error at 24 Months (On-Treatment)**

33 The primary analysis will be a treatment group comparison of mean change from baseline  
34 to 24 months in spherical equivalent refractive error (SER), as measured by a masked  
35 examiner using cycloplegic autorefraction, using a longitudinal discrete time mixed  
36 model. The population-averaged method will be used to model the repeated measures on  
37 SER at 6, 12, 18, and 24-month visit. The time variable will be categorical to not impose  
38 assumptions regarding trend of SER over time. The correlations between SER  
39 measurements within person across visits will be estimated and a correlation structure  
40 will be selected accordingly. (Given that the follow-up visits are approximately equally  
41 spaced, an autoregressive covariance structure is considered likely. Other correlation  
42 structures will also be fitted, and the information criteria will be used to select the most  
43 appropriate covariance structure.) The model will include the interaction between time  
44 and treatment group and adjust for baseline SER, age, iris color (brown vs. non-brown),  
45 and race (East Asian vs. non-East Asian), to account for potential residual confounding,  
46 and improve power for the treatment comparison. The web data entry system mandated  
47 that baseline SER, age, and iris color could not be missing at enrollment. The value  
48 ‘unknown’ will be used in the mixed model for missing race/ethnicity value.

49  
50 Given that at most a small number of participants of East Asian race are expected to have  
51 non-brown iris, there is a possibility of partial aliasing when including both race and iris  
52 color in the mixed model. If the fully-adjusted model fails to converge, or displays  
53 evidence of estimate instability, such as very large standard error associated with a  
54 partially-aliased covariate, the race and iris color variables will be combined as follows:  
55 East Asian (regardless of eye color), non-East Asian with brown eyes, non-East Asian  
56 with non-brown eyes. The number of East Asians with non-brown eye color will be  
57 tabulated and reported.

58  
59 At baseline and all follow-up visits, including the 24-month visit, the mean of the three  
60 readings from autorefraction in each eye will be calculated and the mean of both eyes for  
61 each participant will be used for the analysis. If fewer than 3 readings are available in  
62 each eye, the mean of available readings will be used for each eye to obtain the mean of  
63 both eyes for each participant. If data from only one eye is available, the mean of  
64 readings on that eye will be used for analysis.

66 The mean change from baseline to 24 months in SER in each treatment group and the  
67 treatment group difference (atropine – placebo), together with their corresponding 95%  
68 confidence intervals, will be estimated using the mixed model with maximum likelihood  
69 estimation. Maximum likelihood estimation gives unbiased estimates of treatment effect  
70 in the presence of missing outcome data, as long as the missing data is missing at random  
71 (MAR) conditional on the variables included in the analysis model. The 2-sided null  
72 hypothesis of mean treatment difference equals zero (superiority hypothesis) will be  
73 tested at an alpha level of 0.05.

### 74 **1.1.Principles to be Followed in Primary Analysis**

75 Model assumptions for the longitudinal discrete time mixed model will be assessed,  
76 including linearity of the adjustment covariates (baseline SER and baseline age), and  
77 normality and homoscedasticity of the outcome distribution across the treatment groups.  
78 The linearity assumption of the baseline covariates of SER and age will be evaluated  
79 using descriptive scatterplots and by categorizing each of the baseline factors in the  
80 model to check for approximate linearity of the coefficients across ordered categories. A  
81 baseline covariate will be included as a continuous variable in the model if the  
82 assumptions for linearity are met for that covariate; otherwise it will be categorized. The  
83 median split will be used for categorization.

84  
85  
86 The primary analysis will follow the intent-to-treat principle; all randomized participants  
87 will be included in the analysis and analyzed according to their randomized treatment  
88 group regardless of whether the assigned treatment was actually received. However, only  
89 data from exams completed within a visit analysis window ( $\pm 3$  months from the expected  
90 visit date) will be included in the analysis. Given that a discrete time model will be used  
91 and the time points will be grouped into 6-month intervals (i.e. 6, 12, 18, or 24 months  
92 from randomization), if two consecutive visits are within 90 days from each other, only  
93 one of the two visits will be included in the analysis. The following principles will be  
94 used in choosing which visit to be included:

- 95 a. If a 24-month primary outcome visit is available, it will be included in the analysis.
- 96 b. Any other visit that is within 90 days of the 24-month visit will be excluded from the  
97 analysis.
- 98 c. If any two visits (other than 24-month visit) are within 90 days of each other, the visit  
99 closer to the expected visit date will be included in the analysis, and the other visit  
100 will be excluded.

101  
102 There will be no explicit imputation of outcome data for exams not completed or  
103 completed outside the analysis window, as the mixed model will produce an unbiased  
104 estimate of treatment effect as long as missing outcome data are missing at random  
105 (MAR), and it is expected that including the baseline covariates and outcome data from  
106 interim follow-up exams in the analysis model is likely to meet MAR requirements,  
107 although this will not be verifiable. Hence, the sensitivity of results to the MAR  
108 assumption will be explored in sensitivity analyses (Section 1.2).

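### If age or baseline SER looks non-linear, the SAP falls back on a median split, which for most smooth one-directional curves fits worse than the straight line it replaces (minor, precision only)

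*SAP*

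**What the plan says.** Section 1 of the SAP adjusts the longitudinal primary model for baseline SER, age, iris colour and race, partly to gain power for the treatment comparison. Age and baseline SER are the two continuous covariates. The population is "aged 5 to less than 13 years with myopia -1.00D to -6.00D at the time of enrollment", so both cover a wide range.

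Section 1.1 checks their linearity with scatterplots and by categorising each factor in the "model to check for approximate linearity of the coefficients across ordered categories. A" covariate stays continuous if the "assumptions for linearity are met for that covariate; otherwise it will be categorized. The" next sentence then fixes the form: the "median split will be used for categorization". No numeric criterion for failure is given, and no other form (polynomial, spline, finer categories) is offered.

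Section 2 carries the Section 1 approach over to 30 months. The 24-month ANCOVA in Section 1.2 lists the same covariates but expressly imports only the aliasing rule. The revision history for version 2.1 says that the ANCOVAs adjust for baseline factors as specified for the primary analysis. Whether the fallback also applies there is therefore not settled.

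**The concern.** The check and the remedy do not match. Seeing a departure from linearity across ordered categories takes at least three groups, because two points always lie on a line. The remedy has two groups. It spends the same single slope parameter as the line, treats all children on one side of the median as alike, and cannot bend.

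The covariates are in the model partly to improve power. If the fallback usually explains less than the line, the rule works against that purpose in the very cases where it acts. At stake is the width of the confidence interval for the treatment difference, and a little power. Bias is not at stake: under randomisation a poorly fitted baseline covariate does not shift the treatment estimate.

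**Working it through.** The SAP gives no sample size, SD or covariate effect, so there is no planned figure to reproduce. Inputs from the SAP: age range 5 to under 13 years, SER range -1.00 to -6.00 D, two-sided alpha 0.05. Assumed: age uniform over its range, age explaining R² = 5 to 20% of outcome variance, and 80% power before the loss.

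**Step 1. Share of the age effect captured** (least-squares R² of each form against the true curve):

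| True curve | Line | Median split | Quadratic |
|---|---|---|---|
| Exponential decay, 0.1 per year | 0.99 | 0.74 | at least 0.99 |
| Exponential decay, 0.4 per year | 0.86 | 0.60 | 0.99 |
| Plateau from age 9 | 0.80 | 0.60 | 0.99 |
| Steep sigmoid at the median (4 per year) | 0.84 | 0.95 | 0.84 |
| Step at the median | 0.75 | 1.00 | 0.75 |
| Symmetric U | 0.00 | 0.00 | 1.00 |

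The ordering is not special to these curves. Among random monotone mixtures of logistic curves the line beat the split in 99.9%. With ages bunched near 10 (SD 1.8), decay curves give 0.85 to 0.99 for the line and 0.46 to 0.64 for the split.

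**Step 2. Effect on variance and power.** The residual variance with a given form is proportional to 1 − R² × share. The variance ratio is therefore V = (1 − R² × split share) / (1 − R² × comparator share), and power becomes Φ(2.80/√V − 1.96), where 2.80 = 1.96 + 0.84.

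Against the line:

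- Plateau, R² 5%: 0.970/0.960 = 1.010; power 79.6%.
- Plateau, R² 20%: 0.880/0.840 = 1.048; power 78.1%.
- Steep decay, R² 5%: 0.970/0.957 = 1.014; power 79.5%.
- Steep decay, R² 20%: 0.880/0.828 = 1.063; power 77.6%.

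Against the quadratic:

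- Steep decay or plateau, R² 5%: 0.970/0.9505 = 1.021; power 79.2%.
- Steep decay or plateau, R² 20%: 0.880/0.802 = 1.097; power 76.3%.

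So for these one-directional curves the loss is about 0.4 to 2.5 points against the line and up to about 4 points against a quadratic. For a step at the median the sign reverses: at R² 20% the ratio is 0.80/0.85 = 0.94, in favour of the split.

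**Step 3. Baseline SER.** Section 1 frames the estimand as change ("The primary analysis will be a treatment group comparison of mean change from baseline") but describes the model with the words "The population-averaged method will be used to model the repeated measures on" SER. With a linear baseline SER term the two responses give the same treatment difference. After a split they need not. If SER itself were the response, the spread of baseline SER inside each half would stay in the error. For a uniform distribution each half is 2.5 D wide, so that variance is 2.5²/12 = 0.52 D². If change is the response and is unrelated to baseline SER, the split costs nothing: the simulated variance ratio was 1.00.

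**The case against.** The strongest case against is that this is small and conditional. It arises only if linearity is judged to fail. An approximate check would usually pass a mild curve and keep the line, whereas a step-like shape, which readily fails, favours the split. That stands. How often the rule would fire cannot be worked out, because the SAP gives no criterion. It limits the weight of the point, but it does not make the split a good remedy for a smooth curve.

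Two stronger readings are tempting.

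- *Power collapses if baseline SER is split.* With SER as the response and an assumed change SD of 0.5 D, the variance ratio would be (0.25 + 0.52)/0.25 = 3.1, and 80% power would become about 36%. This needs raw SER as the response and also a failed linearity check for baseline SER. Sections 1, 1.2 and 2 repeatedly state the comparison as change. If SER were modelled, follow-up SER should track baseline SER closely, so the check would seldom fail; in simulation with a proxy test (p < 0.05) it failed in 2% of trials without curvature and 3 to 30% with assumed curvature. The figure is no basis for the point.
- *The model needs age by visit.* Section 1 names only the time-by-treatment interaction, so on a plain reading age has one coefficient for all visits. Main-effect covariates are nevertheless valid. Section 4 says that younger children are earlier in progression but gives no size. Under the autoregressive structure that Section 1 thinks likely, the assumed loss with linear build-up is 0.3 to 1.4 power points. The ANCOVA in Section 1.2 already gives age a 24-month coefficient. This is a modelling preference and no change is asked for.

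**Conclusion.** The point holds in a limited form. The median-split fallback is a poor choice for most smooth one-directional covariate curves: it usually explains less than the line it replaces and clearly less than a quadratic. The sizes above rest on an assumed age distribution, assumed curves and an assumed age R² of 5 to 20%, none of which the SAP gives. Nothing in the document shows that the fallback was or will be triggered. The severity is minor.

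**What to change.** In Section 1.1, replace the median-split fallback by a quadratic term or a 3-knot restricted cubic spline for the covariate that fails the check. Use the same form in the primary and 30-month mixed models, and in the 24- and 30-month ANCOVAs if the fallback is applied there. Do not dichotomise baseline SER.

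The cost is one extra parameter per affected covariate, and only if the check fails. A quadratic fits worse than the split if the truth is a step at the median (0.75 against 1.00 in the table). The main cost is timing. Version 2.1 is dated November 28, 2022, and Section 7 expected all 24-month data by December 2021, so this would be a late change to the primary model and should be disclosed as such. If the linearity check has already been run, report its result and show the treatment difference under both forms.

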### 109 **1.2.Sensitivity Analysis**

112 A sensitivity analysis will be conducted to compare the mean change in SER from  
113 baseline to 24 months between the treatment groups using an analysis of covariance  
114 (ANCOVA) model, adjusting for baseline SER, age, iris color (brown vs. non-brown),  
115 and race (East Asian vs. non-East Asian). Possible partial aliasing of iris color and race  
116 will be handled as specified for the primary analysis model.  
117  
118

## 119 **2. Secondary Objective: Efficacy off Atropine Treatment (30 Months)**

120 The secondary objective is to determine the efficacy of atropine treatment for slowing  
121 progression of myopia after a period of 6 months off treatment. The same approach  
122 defined in Section 1 (including the sensitivity analysis) will be used to obtain a treatment  
123 group comparison of change from baseline to 30-months in SER, as measured by a  
124 masked examiner using cycloplegic autorefraction. The mean treatment group difference  
125 and the corresponding 95% confidence interval will be estimated at 30 months. However,  
126 the statistical testing of significance will be performed only if a statistically significant  
127 effect for treatment was found in the primary analysis at 24 months.  
128

129 30-month visits will be included in the analysis as long as they are no earlier than 3  
130 months and no later than 6 months from the expected visit date and same follow-up SER  
131 measurements selected for the primary analysis (at 6, 12, 18, or 24 months from  
132 randomization) using the principles specified in Section 1.1 will be included in the  
133 analysis.  
134  
135

136 A sensitivity analysis will be conducted to compare the mean change in SER from  
137 baseline to 30 months between the treatment groups using an ANCOVA model, adjusting  
138 for baseline SER, age, iris color (brown vs. non-brown), and race (East Asian vs. non-  
139 East Asian).  
140  
141

## 142 **3. Secondary Outcomes**

143 The overall false discovery rate (FDR) in the secondary analyses specified in Section 3  
144 below will be controlled at the 5% level using the two-stage step-up false discovery rate  
145 procedure of Benjamini, Krieger, and Yekutieli. This involves first applying the false  
146 discovery rate procedure of Benjamini and Hochberg at alpha level = (overall  $\alpha$ )/(overall  
147  $\alpha + 1$ ) to estimate the number of true null hypotheses, and then applying the adaptive  
148 FDR adjustment conditional on the number of true null hypotheses. This method  
149 generally has better power than the usual Benjamini-Hochberg FDR method.  
150  
151

